| 8.4 Procedure for Handling Deviation of Report from the Original Statistical Plan | 22 |
| 9. Risk-Benefit Analysis | 22 |
| 9.1 Benefits of the Study | 22 |
| 9.2 Risks of the Study | 22 |
| 10. Feasibility Analysis of the Trial | 23 |
| 11. Quality Control of the Clinical Trial | 23 |
| 12. Ethical Issues and Informed Consent | 24 |
| 12.1 Ethical Considerations | 24 |
| 12.1.1 Ethics and Regulations | 24 |
| 12.1.2 Medical Ethics Committee | 24 |
| 12.2 Informed Consent Process..... | 25 |
| 13. Provisions for Reporting Adverse Events and Device Defects | 25 |
| 13.1 Definition of Adverse Events and Reporting Requirements | 25 |
| 13.1.1 Severity of Adverse Events | 25 |
| 13.1.2 Event Relationship to the Investigational Device | 25 |
| 13.1.3 Adverse Event Record | 26 |

| | |
|---|----|
| 13.2 Device Defects..... | 26 |
| 13.3 Definition of Serious Adverse Events..... | 27 |
| 13.4 Reporting Procedures and Contact Information..... | 27 |
| 13.4.1 SAE Reporting Procedure | 27 |
| 13.4.2 Device Defect Reporting Procedure | 27 |
| 14. Deviations from the Clinical Trial Protocol and Provisions for Modification of the Protocol . | 28 |
| 14 Deviations from the Clinical Trial Protocol | 28 |
| 14 Provisions for Modifications of the Clinical Trial Protocol | 28 |
| 15. Direct Access to Source Data and Files | 29 |
| 16. Contents Covered by the Clinical Trial Report..... | 29 |
| 17. Confidentiality | 29 |
| 18. Agreement on Publication of Trial Results..... | 30 |
| 19. References: | 30 |

Protocol Summary

| | |
|--|--|
| Study Title | Real-World Clinical Study on the Efficacy of Disposable Gastrointestinal Vibrating Capsule (Vibrabot Capsule) for Chronic Functional Constipation |
| Study Purpose | Through this real-world study, to analyze the response of functional constipation patients with different severity, treatment status, capsule dosage, and combined medication to Vibrabot capsule, as well as the duration of efficacy maintenance during the follow-up period; to compare the efficacy with patients treated with drugs or other therapies during the same period, explore the possibility of curing functional constipation patients, further improve the treatment satisfaction of constipation patients, and promote the establishment and application of consensus or guidelines for the use of Vibrabot capsule in treating functional constipation. |
| Investigational Device | Device Name: Disposable Gastrointestinal Vibrating Capsule (Vibrabot Capsule) Model: ADVC-3 Manufacturer: ANKON Medical Technologies (Shanghai) Co., Ltd. |
| Study Population | Patients with chronic functional constipation |
| Number of Subjects to be Included | 300 |
| Study Design | This study is a multi-center prospective cohort study, which plans to include 300 patients with chronic functional constipation to treat with Vibrabot capsules, and at the same time, include ≥ 300 patients receiving constipation treatment during the same period. During the study, it is necessary to collect the patients' basic |

| | |
|---------------------------------------|--|
| | 
information, baseline constipation status and treatment information, capsule intake during treatment, and concomitant medication. During the treatment phase, patients follow the doctor's advice to receive Vibrabot capsule treatment and maintain stable dietary intake and exercise according to the constipation diagnosis and treatment guidelines.
 
During the study, patients need to scan the QR code or search for the electronic questionnaire "Vibrabot Health" Official Account on WeChat, and fill in the relevant information during the treatment in the electronic questionnaire in a timely and truthful manner. The treatment effect of the patients is evaluated by assessing the number of occurrences of spontaneous bowel movements (SBM) and complete spontaneous bowel movements (CSBM).
 |
| 
Primary Endpoints
 | 
After treatment, whether the response rate of patients using the Vibrabot vibrating capsules alone reaches 50%.
 
The definition of the responder is a patient with an average weekly increase of ≥ 1 complete spontaneous bowel movement (CSBM) compared to the baseline.
 |
| 
Secondary Endpoints
 | 
 1) Proportion of constipated patients who use/do not use other constipation treatment methods during treatment and after the vibrating capsule treatment and at the end of follow-up; 2) Proportion of patients with an average increase of ≥ 1 CSBMs per week compared to the baseline period; 3) Proportion of respondents with an average of ≥ 3 SBMs per week during the treatment period; 4) Proportion of subjects with ≥ 3 SBMs per week and an increase of ≥ 1 CSBMs during at least 4 weeks of treatment compared to baseline; 5) Proportion of patients with an average increase of ≥ 1 CSBMs per |

| | |
|-------------------------|--|
| | 
week during the follow-up phase compared to the baseline period;
 
6) Proportion of patients with an average of ≥ 3 SBMs per week during the follow-up phase;
 
7) Proportion of patients with a reduction of ≥ 1 point in total PAC-QOL and PAC-SYM scores after treatment compared to the baseline period;
 
8) Proportion of patients with a reduction of ≥ 1 point in total PAC-QOL and PAC-SYM scores after follow-up compared to the baseline period;
 
9) Time of first use of laxative or enema after a course of vibrating capsule treatment (6 weeks);
 
10) Proportion of constipated patients (including different constipation types, occupations, age groups, BMI, gender, and baseline treatment status) responding to vibrating capsule treatment and at the end of follow-up.
 |
| Safety Endpoints | 
 1. The incidence (%) and the number of device-related adverse events (AEs) and serious adverse events (SAEs); 2. The incidence (%) and the number of device defects. |

1. About the Sponsor

| | |
|--------------|---|
| Name: | ANKON Medical Technologies (Shanghai) Co., Ltd. |
| Address: | [name] |
| Contact No.: | [name] |

2. List of All Clinical Trial Sites and Investigators in the Multi-Center Clinical Trial

| Site No. | Clinical Trial Site Name | Principal Investigator | Professional Title |
|----------|---|------------------------|----------------------------|
| 01 | The First Affiliated Hospital of Navy Medical University (Shanghai Changhai Hospital) | [name] | Chief Physician, Professor |

| | | | |
|----|---|----------------|----------------------------|
| 02 | Ruijin Hospital, Shanghai Jiao Tong University School of Medicine | [name] | Chief Physician, Professor |
| 03 | Shanghai Tongji Hospital | [name] | Chief Physician |
| 04 | Shanghai Tenth People's Hospital | [name] | Chief Physician, Professor |
| 05 | Shanghai First People's Hospital | [name] | Chief Physician |
| 06 | Shanghai Sixth People's Hospital | [name] | Chief Physician, Professor |
| 07 | Shanghai Ninth People's Hospital | [name] | Chief Physician |
| 08 | Shanghai Yangpu District Central Hospital | [name] | Chief Physician |
| 09 | Shanghai Pudong New Area Gongli Hospital | [name] | Chief Physician |

3. Purpose and Content of the Clinical Trial

3.1 Purpose of the Clinical Trial

Through this real-world study, to analyze the response of functional constipation patients with different severity, treatment status, capsule dosage, and combined medication to Vibrabot capsule, as well as the duration of efficacy maintenance during the follow-up period; to compare the efficacy with patients treated with drugs or other therapies during the same period, explore the possibility of curing functional constipation patients, further improve the treatment satisfaction of constipation patients, and promote the establishment and application of consensus or guidelines for the use of Vibrabot capsule in treating functional constipation.

3.2 Content of the Clinical Trial

This study is a multi-center clinical trial. Patients are considered eligible for this study if they meet the inclusion criteria and do not meet any of the exclusion criteria. This study plans to include 300 patients with chronic functional constipation to treat with Vibrabot capsules for at least 6 weeks, and ≥ 300 patients with constipation receiving

other treatments concurrently. The patients, based on their treatment needs and preferences, and after comprehensive consideration by clinical doctors, will undergo vibrating capsule treatment, other treatments, or combination therapy. After entering the study, patients should maintain stable dietary intake (including high-fiber diet, fiber supplements, probiotics, etc.) and exercise according to the recommendations of the constipation diagnosis and treatment guidelines.

During the entire clinical study period, patient-related information will be collected according to the specified time points in the protocol to evaluate the response of functional constipation patients with different severity levels to Vibrabot capsules.

Patients are considered eligible for this study if they meet the inclusion criteria and do not meet any of the exclusion criteria. This study plans to include 300 patients with chronic functional constipation to treat with Vibrabot capsules for at least 6 weeks or more.

The patients, based on their treatment needs and preferences, and after comprehensive consideration by clinical doctors, will undergo vibrating capsule treatment. After entering the study, patients should maintain stable dietary intake (including high-fiber diet, fiber supplements, probiotics, etc.) and exercise according to the recommendations of the constipation diagnosis and treatment guidelines.

4. Background of the Clinical Trial

Constipation is characterized by a decrease in bowel movements, dry and hard stools, and difficulty in defecation. With changes in diet, faster pace of life, and social psychological factors, the prevalence of chronic constipation is on the rise. The global incidence of chronic constipation is 14%, while the prevalence of chronic constipation in adults in China is 4.0% to 10.0%. The prevalence of functional constipation in China is 6%. The high-risk groups for constipation include the elderly, women,

diabetics, those taking opiates, antipsychotic drugs, or bedridden patients. Occupation, lifestyle, dietary habits, mental health, family history of constipation, and BMI are factors related to constipation.

Constipation affects patients' quality of life, and some patients abuse laxatives or repeatedly seek medical treatment, increasing medical costs. The main treatments for constipation are adjusting lifestyle, medication, psychotherapy, biofeedback, and surgery. However, these methods often have side effects, and patient satisfaction is still relatively low. A new approach needs to be explored to address this clinical problem.

The Disposable Gastrointestinal Vibrating Capsule System (Vibrabot capsule) (NMPA Device Approval No. 20223090282) is the world's first approved and marketed product for treating constipation through purely physical means. It can provide intermittent comfortable massages to the digestive tract, activate the intestinal neural network, awaken intestinal motility, and help alleviate constipation issues. Clinical study results show that the product is safe to use and can increase the frequency of bowel movements in patients with chronic functional constipation. This study focuses on post-marketing clinical study for patients with functional constipation of varying severity, further evaluating the efficacy of the product in a large sample population.

5. Product Features, Composition, Working Principle, and Action Mechanism

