7.1 Trial Procedure

7.1.1 Trial Flow Chart

| | Visit 1 (0~1 day) | Visit 2 (Week 2 ±3 days) | Visit 3 (Week 4 ±3 days) | Visit 4 (Week 6±3 days) | Visit 5 (Week 10 ±3 days) |
|--|-------------------|--------------------------|--------------------------|-------------------------|---------------------------|
| Informed Consent | X | | | | |
| Baseline Information | X | | | | |
| Inclusion/Exclusion Criteria | X | | | | |
| Prescription Vibrabot capsule treatment/Medication treatment | X | X | X | | |
| Guide patients to use the "Vibrabot Health" Official Account | X | | | | |
| Fill out the Baseline Period Questionnaire (including scale) in the Official Account | X | | | | |
| Fill out the Daily Bowel Movement Questionnaire and Constipation Symptom Self-Assessment Scale and Assessment Scale for Quality of Life with Constipation | | X | X | X | X |
| Concomitant treatment | X | X | X | X | X |
| Adverse event | X | X | X | X | X |

正常诊疗流程筛选入组
Screening for Inclusion Based on Normal Diagnosis and Treatment Procedure

| | | | | | |
|--|---|---|---------------------------------------|---|-------|
| 功能性便秘分型(结肠传输时间、肛门直肠测压等) Functional Constipation Subtyping (Colon Transit Time, Anorectal Manometry, etc.) | 通过症状或问诊对便秘分型初步评估 Preliminary Assessment of Constipation Subtype Based on Symptoms or Interview | 可选 Optional | | | |
| 通过评估, 选择其他治疗方法 Selecting Alternative Treatment Methods through Assessment | 使用蔚通胶囊治疗 Treatment with Vibrabot Capsule | | | | |
| 患者填写问卷, 收集数据 Patients Complete Questionnaires to Collect Data | 沪惠保优惠或其他渠道购买 Purchase through Shanghai-Huibo Health Benefits or Other Channels | | | | |
| 不同使用频次 Different Frequency of Use | 不同疗程 Different Treatment Duration | 与其他方法联合治疗 Combination Treatment with Other Methods | 不同严重程度 Various Severity Levels | 对比其他方法治愈 Comparing Treatment Efficacy with Other Methods | |
| 各中心医生端数据共享 Data Sharing among Medical Centers | 定期学术会议讨论 Regular Academic Meetings for Discussion | | | | |
| 蔚通治疗方法不断优化, 形成专家共识 Continuous Optimization of the Vibrabot Treatment Method, Leading to Expert Consensus | 完成总结报告、科技论文, 研究生培养 Completion of Summary Report, Scientific Paper, and Training of Graduate Students | | | | |

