7.1.2 Visit Content

Each patient will undergo a series of study visits, including screening, treatment visit, and follow-up visit. The visit process is briefly described as follows:

Visit 1 (0 ~ 1 day) - Baseline/Screening Period:

This visit includes:

The patient will sign an informed consent form;

Set the inclusion/exclusion criteria;

Guide patients to fill out the questionnaire using the Official Account and complete the *Baseline Period Questionnaire* in the Official Account.

Prescription Vibrabot capsule treatment or other treatment options.

Visit 2 (Week 2 ±3 days) - Treatment Period 1:

This visit includes:

Fill out the *Daily Bowel Movement Questionnaire* in the WeChat Official Account every day, take Vibrabot capsules on time or opt for other treatment plans;

Fill out the *Constipation Symptom Self-Assessment Scale and Assessment Scale for Quality of Life with Constipation* in the Official Account every 2 treatment weeks.

Record adverse events and concomitant treatments;

Prescription Vibrabot capsules or other treatment options.

Visit 3 (Week 4±3 days) - Treatment Period 2

This visit includes:

Fill out the *Daily Bowel Movement Questionnaire* in the WeChat Official Account every day, take Vibrabot capsules on time or opt for other treatment plans;

Fill out the *Constipation Symptom Self-Assessment Scale and Assessment Scale for Quality of Life with Constipation* in the Official Account every 2 treatment weeks.

Record adverse events and concomitant treatments;

Prescription Vibrabot capsules or other treatment options.

Visit 4 (Week 6 ±3 days) - Treatment Period 3

This visit includes:

Fill out the *Daily Bowel Movement Questionnaire* in the WeChat Official Account every day, take Vibrabot capsules on time or opt for other treatment plans;

Fill out the *Constipation Symptom Self-Assessment Scale and Assessment Scale for Quality of Life with Constipation* in the Official Account every 2 treatment weeks.

Record adverse events and concomitant treatments.

Visit 5 (Week 10±3 days) - Follow-up Period:

This visit includes:

Fill out the *Daily Bowel Movement Questionnaire* in the WeChat Official Account every day;

Fill out the *Constipation Symptom Self-Assessment Scale and Assessment Scale for Quality of Life with Constipation* in the Official Account every 2 treatment weeks;

Record adverse events and concomitant treatments.

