7.2 Secondary Efficacy Endpoints

- 1) Proportion of constipated patients who use/do not use other constipation treatment methods during treatment and after the vibrating capsule treatment and at the end of follow-up;
- 2) Proportion of patients with an average increase of ≥ 1 CSBMs per week compared to the baseline period;
- 3) Proportion of respondents with an average of ≥ 3 SBMs per week during the treatment period;
- 4) Proportion of subjects with ≥ 3 SBMs per week and an increase of ≥ 1 CSBMs during at least 4 weeks of treatment compared to baseline;
- 5) Proportion of patients with an average increase of ≥ 1 CSBMs per week during the follow-up phase compared to the baseline period;
- 6) Proportion of patients with an average of ≥ 3 SBMs per week during the follow-up phase;
- 7) Proportion of patients with a reduction of ≥ 1 point in total PAC-QOL and PAC-SYM scores after treatment compared to the baseline period;
- 8) Proportion of patients with a reduction of ≥ 1 point in total PAC-QOL and PAC-SYM scores after follow-up compared to the baseline period;
- 9) Time of first use of laxative or enema after a course of vibrating capsule treatment (6 weeks);
- 10) Proportion of constipated patients (including different constipation types, occupations, age groups, BMI, gender, and baseline treatment status) responding to vibrating capsule treatment and at the end of follow-up.

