8.1 Statistical Analysis of the Population

Sample Size Calculation

H0: The effectiveness rate of vibrating capsule treatment for constipation $\leq 50\%$

H1: The effectiveness rate of vibrating capsule treatment for constipation $> 50\%$

In a single-group design, if the study goal is to evaluate the effectiveness of vibrating capsule

treatment for constipation and compare it with the expected 50% effectiveness rate, then a one-sample proportion test can be considered for sample size calculation.

Sample size calculation formula for single sample proportion test is:

$$n = \frac{\left[Z_{1-\alpha} \sqrt{P_0(1-P_0)} + Z_{\beta} \sqrt{P_T(1-P_T)} \right]^2}{(P_T - P_0)^2}$$

Where:

- (1) p is the overall expected success rate (here it is estimated that the effectiveness of treating constipation with vibrating capsules is 50%);
- (2) p_0 is the success rate under the null hypothesis (assuming a 40% success rate under the null hypothesis);
- (3) The probability of Type I error α is set to 0.05, and the probability of Type II error β is set to 0.2 (i.e., the statistical power is $1-\beta=0.8$);

At least 191 participants are needed for this study. Assuming a 20% loss to follow-up, the final sample size required is 239. Considering this is a real-world study and taking into account the outpatient volume of the participating center, it is planned to enroll 300 patients who will take vibrating capsules for 6 weeks, and at the same time, include ≥ 300 patients undergoing constipation treatment during the same period.

(1) Full Analysis Set (FAS) is the set of patients that is as close as possible to the ideal implied by the Intention-to-Treat principle. Specifically, in this trial, the FAS is the data set of all patients with baseline evaluation who take at least one capsule treatment/other treatment option. Missing data for primary efficacy endpoints in the FAS will be imputed according to certain rules while missing data for secondary efficacy endpoints will not be imputed.

(2) Per Protocol Set (PPS) is a subset of the FAS and refers to the set of subjects who meet the inclusion criteria, do not meet the exclusion criteria, complete the treatment, and have no protocol violations. Specifically, in this trial, the PPS includes the patients in the FAS who:

- a) complete the full treatment,
- b) meet the inclusion criteria and do not meet the exclusion criteria,
- c) have good compliance with capsule administration/other treatment, and

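### Capsule duration is stated inconsistently and the follow-up endpoints carry no off-capsule condition, so use continued past Week 6 could be counted as maintained effect

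*Combined protocol and SAP*

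**What the plan says.** **Passages that leave the duration open.** Section 3.2 of the combined protocol and SAP states it twice. It plans 300 patients "to treat with Vibrabot capsules for at least 6 weeks, and ≥ 300 patients with constipation receiving" other treatments, and then repeats the capsule group as patients "to treat with Vibrabot capsules for at least 6 weeks or more". Neither statement sets a maximum. The Section 7.1.1 flow chart includes "Different Treatment Duration" among its branches, and gives the supply route as "Purchase through Shanghai-Huibo Health Benefits or Other Channels".

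**Passages that point to six weeks.** In Section 8.1, "it is planned to enroll 300 patients who will take vibrating capsules for 6 weeks". Secondary endpoint 9 in Section 7.2 is "Time of first use of laxative or enema after a course of vibrating capsule treatment (6 weeks", with the bracket closing there. In Section 7.1.1 the prescription row is marked at Visits 1, 2 and 3 only. In Section 7.1.2, Visits 2 to 4 tell patients to take capsules; the Visit 5 list does not.

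**Follow-up.** Visit 4 (Week 6 ±3 days) is the third treatment period. The next contact is "Visit 5 (Week 10±3 days) - Follow-up Period". Section 3.1 makes the persistence of the effect in follow-up a study purpose. Endpoints 5, 6, 8 and 10 are measured in or after follow-up; endpoint 6, for example, is "Proportion of patients with an average of ≥ 3 SBMs per week during the follow-up phase". Section 7 says that capsule intake is collected during treatment.

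**The concern.** Persistence after a course is only interpretable if it is known when the course ended. Here the follow-up assessment is tied to the calendar. No passage requires capsules to have stopped by Week 6, links the start of follow-up to the last capsule, or says how a patient still taking capsules between Visits 4 and 5 is to be analysed.

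No other definition separates such patients. The spontaneous-movement definition in Section 7 refers to medication in the preceding 24 hours and sets no off-capsule condition. Endpoint 1 concerns other constipation treatments, so continued capsule use is not clearly captured there. At stake is the durability conclusion, which Section 3.1 places beside exploring cure and supporting guidelines. The open duration also touches the primary endpoint, which is assessed after treatment with no week named, but the main consequence is for the follow-up endpoints.

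**Working it through.** The plan gives no figure for continued use. The numbers attached to the six-week statement in Section 8.1 (191, and 191/0.8 = 238.75, so 239 after 20% loss) do not involve treatment duration and do not bear on the point. The check is therefore a comparison of passages, then two short calculations.

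**1. Passages side by side**

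| Place | What it implies |
|---|---|
| Section 3.2, both statements | Six weeks minimum, no maximum |
| Section 7.1.1 flow chart | Durations differ between patients |
| Section 8.1 | Six weeks |
| Section 7.2, endpoint 9 | Six weeks |
| Section 7.1.1, prescription row | No prescribing after Visit 3 (Week 4) |
| Section 7.1.2, Visit 5 list | Capsule-taking not listed |

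The first two rows allow use after Week 6. The other four describe or imply a six-week course. No passage settles the difference.

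**2. The follow-up window.** The start of follow-up is not defined, so Week 6 to Week 10 is inferred from Visits 4 and 5. Visit 4 falls on days 42 ± 3, that is 39 to 45. Visit 5 falls on days 70 ± 3, that is 67 to 73. The gap runs from 67 − 45 = 22 to 73 − 39 = 34 days. In a nominal four-week window, a patient whose last capsule is at week w (6 to 10) has a share (w − 6)/4 of it on capsules:

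| Last capsule at week | 6 | 7 | 8 | 9 | 10 |
|---|---|---|---|---|---|
| Share of window on capsules | 0% | 25% | 50% | 75% | 100% |

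**3. Size, for illustration only.** Let *q* be the share of patients still taking capsules. Then

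reported follow-up response = off + (on − off) × *q*.

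The on-capsule rate is the plan's 50% expected effectiveness (Section 8.1). The off-capsule rate and *q* are assumptions, because the documents give neither. The example fits endpoint 5 best, since it uses the same increase in complete spontaneous movements as the primary responder definition.

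| Assumed off-capsule rate | *q* = 0 | *q* = 10% | *q* = 25% | *q* = 50% |
|---|---|---|---|---|
| 20% | 20% | 23% | 27.5% | 35% |
| 30% | 30% | 32% | 35% | 40% |
| 40% | 40% | 41% | 42.5% | 45% |

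For example, 0.30 + (0.50 − 0.30) × 0.25 = 0.35. Every continuer is treated as on capsules for the whole window and as responding at the average on-capsule rate. If response were equal on and off capsules, the shift would be zero.

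**4. Endpoint 9.** This is a time to first laxative or enema after a six-week course, not an average over follow-up weeks. The difficulty here is the origin: for a patient who continues, the documents do not say whether time runs from Week 6 or from the last capsule.

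**The case against.** The best reply is that the schedule, which sites will actually follow, describes a six-week course. Prescribing stops at Visit 3, Visit 4 is the last treatment visit, and capsule-taking disappears from the Visit 5 list. On that reading, Section 3.2 merely sets a minimum course for the capsule cohort. The flow-chart entry on duration sits beside frequency, combination and severity, and may only list planned comparisons. The purchase entry says how capsules are bought, not when.

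Much of this stands. A reader might infer from Section 3.2 that patients do continue past Week 6 and that the follow-up endpoints therefore do mix on-capsule and off-capsule weeks. The documents do not support that: no passage says that anyone takes capsules after Week 6. They permit it and provide no rule for it. The schedule does not remove the permission either, because it sets no stopping requirement, the product is marketed, and Section 3.2 gives an open-ended duration twice.

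A second reply is that keeping every patient at a fixed time point is defensible in a real-world study, and that analysing only off-capsule weeks selects on behaviour after baseline and gives unequal windows. A patient stopping at Week 9 would contribute about one week. Continuers might be good or poor responders, so the selection could bias in either direction. This also stands. It argues for keeping the all-patient result and adding a split by continued use.

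**Conclusion.** The documents contradict themselves on capsule duration, and the follow-up endpoints do not say how continued use is handled. Endpoints 5, 6, 8 and 10 could count a patient still on capsules as maintained effect, and endpoint 9 lacks a clear origin for such a patient.

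Upward bias is likely if response is higher on capsules than off. Over the assumed values tabulated, with 10% to 50% continuing, the shift runs from 1 point (off-capsule rate 40%, 10% continuing) to 15 points (off-capsule rate 20%, 50% continuing). A reader might take these as estimates of the bias; they are not, because the number affected and the off-capsule rate are unknown.

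A reader might also assume that the data needed to separate the groups are already collected. Section 7 promises capsule intake only during treatment. The Visit 5 list includes concomitant treatments, but does not say that capsules are entered there. The point concerns secondary endpoints, but they carry a stated study purpose and the remedy is cheap, so it should be addressed.

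**What to change.** - Reconcile the duration statements in Sections 3.2, 7.1.1, 7.1.2, 7.2 (endpoint 9) and 8.1. Which duration is right is for the sponsor.
- Define when the follow-up phase starts, and state the time origin for endpoint 9.
- Record capsule use and the date of the last capsule through Visit 5.
- Report endpoints 5, 6, 8, 9 and 10 for all patients, and separately for those with and without capsule use after Week 6.
- Base any statement about efficacy maintained after stopping on those without such use, noting that this group is selected after baseline.

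The cost is protocol and SAP wording, one extra data item at Visit 5, and a smaller group behind the off-capsule result.
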